6.0 STATISTICAL CONSIDERATIONS

The three clinical endpoints are adverse events (e.g., neuropathy), disease-free survival (DFS) and survival (OS). The exact definitions for these outcomes will be equivalent to those specified in the treatment protocol (CALGB/SWOG C80702). The treatment by biomarker (or genotype) interactions will be tested for the celecoxib hypothesis. If an interaction is present, relevant hypotheses will also be tested in the treatment groups of patients receiving and not receiving celecoxib. If no interaction is present, the treatment groups will be combined (celecoxib + no celecoxib) for analysis. Power estimates for specified differences in interaction are given in Table 3. Table 4 contains power estimates for DFS comparisons of biomarker and genotype within treatment group (celecoxib; no celecoxib) by marker prevalence, detectable hazard ratio and the percent of samples available. Table 5 provides power estimates for testing the prognostic value of a marker when no treatment by marker interaction is present. Table 6 illustrates detectable differences in DFS for biomarkers quantified in quartiles. Table 7 illustrates the difference detectable with the specified power for a biomarker quantified in quartiles versus a dichotomous marker; for example, Vitamin D levels measured by plasma 25(OH)D versus K-ras mutational status. Tables 8 and 9 describe the power achieved to detect the illustrated difference in Grade 3+ toxicity rates versus a biomarker quantified in quartiles. Examples are Grade 3+ neutropenia and diarrhea versus body mass index.

Table 3. Approximate power to detect the specified hazard ratio for treatment (no celecoxib; celecoxib) by biomarker interactions with 60% (n=1,500) and 80% (n=2,000) of samples obtained (2-sided $\alpha=0.1$) assuming exponential survival, a dichotomous biomarker, equal sample sizes per group, and an overall event rate of 0.31 (775/2500).

n (events)	Hazard Ratio-Interaction	Power
	1.5	
1500 (465)		0.34,0.58,0.71
2000 (620)		0.47,0.71,0.81
	1.6	
1500 (465)		0.48,0.71,0.81
2000 (620)		0.63,0.83,0.90
	1.7	
1500 (465)		0.60,0.81,0.88
2000 (620)		0.76,0.91,0.95

Moderate to large interaction hazard ratios are detectable with adequate power.

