Table 4. Power estimates for DFS comparisons of a dichotomous biomarker or genotype within treatment groups (e.g., patients receiving celecoxib) by marker prevalence, detectable hazard ratio and the percent of samples available (log rank test, 2-sided $\alpha=0.01, 0.05, 0.10$). Exponential survival, equal numbers of samples per treatment arm, and an overall event rate of 0.31 (775/2500) are assumed.

	Detectable Hazard Ratio	1.4	1.5	1.6
Marker/Genotype Prevalence	n (number of events)			
0.5				
	750 (233)	0.49,0.72,0.82	0.69,0.87,0.92	0.84,0.94,0.97
	1000 (310)	0.65,0.84,0.90	0.83,0.94,0.97	0.94,0.98,0.99
0.2				
	750 (233)	0.30,0.53,0.65	0.46,0.69,0.79	0.61,0.81,0.88
	1000 (310)	0.41,0.65,0.76	0.61,0.81,0.88	0.76,0.91,0.95
0.1				
	750 (233)	0.15,0.33,0.45	0.23,0.45,0.58	0.33,0.57,0.69
	1000 (310)	0.21,0.42,0.55	0.33,0.57,0.69	0.46,0.69,0.79

Adequate power is achieved to detect moderate to large hazard ratios for dichotomous biomarkers or genotypes with prevalence close to 50%. The power estimates at 50% prevalence are approximately correct for biomarkers or genotypes with prevalence $\geq 30\%$ and $\leq 70\%$. For biomarkers or genotypes with prevalence near 20% and, in particular, 10%, larger differences are detectable with adequate power.

Table 5. Power estimates for DFS comparisons of a dichotomous biomarker or genotype by marker prevalence for all patients, detectable hazard ratio, and the percent of samples available (log rank test, 2-sided $\alpha=0.01, 0.05, 0.10$). Exponential survival and an overall event rate of 0.31 (775/2500) are assumed.

	Detectable Hazard Ratio	1.2	1.3	1.4	1.5
Marker/Genotype Prevalence	n (number of events)				
0.5					
	1500 (465)	0.27,0.50,0.62	0.59,0.80,0.88	0.85,0.95,0.97	0.96,0.99,0.99
	2000 (620)	0.37,0.62,0.73	0.75,0.90,0.94	0.94,0.98,0.99	0.99,0.99,0.99
0.2					
	1500 (465)	0.15,0.34,0.47	0.37,0.61,0.73	0.62,0.82,0.89	0.82,0.93,0.96
	2000 (620)	0.22,0.44,0.56	0.51,0.74,0.83	0.78,0.91,0.95	0.92,0.98,0.99
0.1					
	1500 (465)	0.08,0.21,0.32	0.18,0.39,0.52	0.034,0.58,0.70	0.51,0.74,0.83
	2000 (620)	0.11,0.27,0.38	0.26,0.49,0.62	0.47,0.71,0.80	0.67,0.85,0.91

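### Appendix II makes arm-specific marker tests depend on finding an interaction, at an unstated level and with limited power, so a marker that acts in one celecoxib arm only can be reported as prognostic for all patients

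*Combined protocol and SAP*

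**What the plan says.** Appendix II, section 6.0, gives the rule in three steps.

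- The test: "The treatment by biomarker (or genotype) interactions will be tested for the celecoxib hypothesis".
- If it finds something: "If an interaction is present, relevant hypotheses will also be tested in the treatment groups of patients receiving and not receiving celecoxib".
- If it does not: "If no interaction is present, the treatment groups will be combined (celecoxib + no celecoxib) for analysis".

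The pooled analysis then has a stated use: "Table 5 provides power estimates for testing the prognostic value of a marker when no treatment by marker interaction is present". Table 4 covers marker comparisons within one celecoxib group.

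Neither the rule nor the text around it gives a significance level, a confidence-interval criterion or a bound that would define absence of interaction. Table 3 gives the power of the interaction test. For an interaction HR of 1.5 its cells read "0.34,0.58,0.71" (1,500 samples, 465 events) and "0.47,0.71,0.81" (2,000 samples, 620 events). The caption names a single two-sided alpha of 0.1, although each cell holds three powers. The captions of Tables 4 and 5 list three levels: 0.01, 0.05 and 0.10.

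Section 5.0 of Appendix II and section 5.1 of Appendix III plan related analyses that do not depend on this rule; they are taken up under the objection.

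**The concern.** The plan speaks of an interaction being present or not, but what it will have is a test result. With no other criterion given, the natural reading is that a non-significant test counts as no interaction. That treats failure to detect a difference between the arms as evidence that there is none, and Table 3 shows that the test often fails to detect a sizeable one.

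When it fails, the pooled marker HR averages two different effects and is presented as prognostic value. A marker that matters only under celecoxib, or only under placebo, could be reported as prognostic for every patient.

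The plan has at least one hypothesis for which this matters directly. Appendix II, section 2.1, predicts that celecoxib-treated patients with low 15-PGDH in normal tissue will have worse disease-free and overall survival than those with high levels. That is a marker effect within one arm, and section 6.0 commits to testing it there only if the interaction test succeeds.

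**Working it through.** **Inputs from the plan.** Events d = 465 (60% of samples) or 620 (80%), from an event rate of 0.31 (775/2500). Table 3 assumes equal group sizes, so arms are 1:1 and marker prevalence is p = 0.5. Interaction HR 1.5, ln(1.5) = 0.4055.

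**Step 1: reproduce Table 3.** The standard error of the log interaction HR is sqrt(4 / (d p (1 − p))), which is sqrt(16/d) at p = 0.5. Power is Φ(0.4055/SE − z), with z = 2.576, 1.960 or 1.645 for two-sided alpha 0.01, 0.05 or 0.10.

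| Events | SE | 0.4055/SE | Power at 0.01 / 0.05 / 0.10 | Table 3 |
|---|---|---|---|---|
| 465 | 0.1855 | 2.186 | 0.348 / 0.589 / 0.706 | 0.34 / 0.58 / 0.71 |
| 620 | 0.1606 | 2.524 | 0.479 / 0.714 / 0.810 | 0.47 / 0.71 / 0.81 |

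All 18 entries of Table 3 reproduce within 0.02 in this way. One-sided levels give 0.444 / 0.706 / 0.817 at 465 events and do not fit. The three powers are therefore for two-sided 0.01, 0.05 and 0.10, and the captioned level fits only the third.

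**Step 2: misses (1 − Table 3 power), interaction HR 1.5.**

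| Events | alpha 0.10 | alpha 0.05 | alpha 0.01 |
|---|---|---|---|
| 465 | 29% | 42% | 66% |
| 620 | 19% | 29% | 53% |

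**Step 3: what pooling then reports.** The documents give no one-arm scenario. I assume marker HR 1.5 in one arm, 1.0 in the other, p = 0.5, and a pooled test at two-sided 0.05.

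- Pooled log HR = 0.5 × 0.4055 = 0.2027, so pooled HR ≈ 1.22.
- Pooled SE = sqrt(4/d) = 0.0927 (465) or 0.0803 (620). The same formula gives 0.27 / 0.50 / 0.63 for HR 1.2 at 465 events; Table 5 has 0.27 / 0.50 / 0.62.
- Pooled power = Φ(0.2027/SE − 1.960) = 0.589 (465) or 0.714 (620).
- With equal variances in the two arms, the average and the difference of the two log HRs are independent, so the joint probability is miss × pooled power, using the unrounded misses from Step 1.

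| Events | Interaction alpha | Miss | Pooled power | Missed and pooled significant |
|---|---|---|---|---|
| 465 | 0.10 | 0.294 | 0.589 | 17% |
| 620 | 0.10 | 0.190 | 0.714 | 14% |
| 465 | 0.05 | 0.411 | 0.589 | 24% |
| 620 | 0.05 | 0.286 | 0.714 | 20% |

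An exponential survival simulation of the same scenario (4,000 runs) gives somewhat higher values: 20% and 15% at alpha 0.10, 28% and 22% at 0.05. The table above is the more cautious version.

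**Step 4: sensitivity.** Table 3 uses the most favourable prevalence. At 18% (the PIK3CA mutation frequency quoted in Appendix IV, section 4.3), SE = 0.2414 or 0.2091, and the test misses 49% / 38% at alpha 0.10 and 61% / 51% at 0.05 (465 / 620 events). With the reduced target of 696 events in protocol section 13.1, 60% of samples gives about 418 events; at 50% prevalence the misses are 33% at 0.10 and 46% at 0.05.

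**The case against.** The best defence is that much of what is needed is already planned outside the rule. For the tumour markers of Objective 1.1, Appendix II section 5.0 fits the marker-by-celecoxib product term and gives celecoxib HRs with 95% confidence intervals in each marker category, whatever the p-value. The ratio of celecoxib HRs between marker levels is the same parameter as the ratio of marker HRs between arms, so a one-arm marker would leave a visible trace. Section 5.0 has similar provisions for plasma analytes by tertile, for modification of the 25(OH)D and CIMP associations by treatment assignment, and for the TIPC subtypes, which are stratified by celecoxib. Appendix III, section 5.1, does the same for candidate SNPs. All of this stands and softens the concern. What none of these provisions gives for markers generally is the marker's own HR in each arm, which is what Table 4 is about and what section 6.0 makes conditional.

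Several stronger readings are tempting and not supported.

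- A reader might infer that after a non-significant test nothing but the pooled result may be shown. Section 6.0 says the arm tests are done in addition when an interaction is found; it does not forbid arm-specific results.
- A reader might infer that the rule defeats the purpose of Appendix II. Objectives 1.1, 1.2 and 1.6 ask whether markers change celecoxib efficacy, and the interaction analyses answer that directly. Objectives 1.3, 1.5 and 1.7 are prognostic, and an average over 1:1 randomised arms is a legitimate estimate if it is called an average.
- A reader might take 42% as the plan's miss rate or its upper limit. It belongs to alpha 0.05 at 465 events. The captioned level gives 29%, the strictest level 66%, and the rule itself names none.
- A reader might rest the case on false positives. With no marker effect, the two-step rule gives some false marker claim in about 8% (interaction alpha 0.05) or 9% (0.10) of studies. But always testing two arm HRs, their ratio and a pooled HR at 0.05 gives at least one in about 13%. Error control is therefore not the argument, and the arm-specific estimates should be descriptive.
- A reader might want a fixed equivalence margin before a marker is called prognostic. A margin of 1/1.5 to 1.5 is unworkable here. With a true ratio of 1 and 50% prevalence, the 95% interval lies inside it in only 18% (465 events) or 43% (620) of studies. At 18% prevalence it never can, because the interval extends by a factor of exp(1.96 × SE) = 1.61 or 1.51 on each side.

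**Conclusion.** The point holds as a weakness of interpretation and reporting. Section 6.0 lets an interaction test with no stated level decide whether marker effects are tested by arm, and reads the pooled effect as prognostic when that test finds nothing.

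The miss rates rest on Table 3 alone and on its assumption of equal groups; lower prevalence or fewer events makes them worse. The figures of 14-17% and 20-24% also rest on my one-arm scenario and a pooled test at 0.05, so they illustrate the mechanism and do not predict how often it will occur. That a non-significant test is what counts as no interaction is the natural reading, but it is an inference, since the plan does not say.

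Only companion analyses are affected. The celecoxib comparison on disease-free survival and the trial's primary conclusion are not. This is a cheap improvement.

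**What to change.** In Appendix II, section 6.0, replace the two conditional sentences with one rule. For each candidate marker, and whatever the interaction p-value, fit one Cox model with celecoxib, marker and their product, and report:

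1. the marker HR with 95% confidence interval in the celecoxib arm and in the placebo arm;
2. the ratio of the two HRs with 95% confidence interval;
3. a pooled marker HR stratified by treatment, described as an average over the arms.

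Add that a marker will not be described as acting equally in both arms solely because the interaction is non-significant. State the level of the interaction test, and label the three powers in Table 3 as two-sided alpha 0.01, 0.05 and 0.10. No fixed equivalence margin is needed.

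The cost is a few sentences and one extra output per marker, with no new data. There will be more arm-specific estimates, to be treated as descriptive, and the wording on prognostic value in all patients will have to be more cautious.

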with prior studies. In secondary analyses, we will examine how the relationship between 25(OH)D level and patient outcome is modified by relevant covariates such as ECOG performance status, treatment assignment, physical activity and body mass index, among others. Tests for statistical interaction will be performed by entering into the model the cross-product term of the plasma 25(OH)D as a continuous variable with the covariate as a continuous or binary variable.

For the analysis of tumoral alterations in vitamin D and related pathways (**Objective 1.4**), all patients who had a tumor block available for analysis of VDR expression, 1- α -hydroxylase, and KRAS mutation and data on circulating 25(OH)D concentration will be included. Tumoral protein overexpression will be defined as a) moderate/strong staining in any fraction of cells, or b) $\geq 50\%$ of tumor cells with weak staining. All tumors will be categorized as having VDR and 1- α -hydroxylase overexpression versus no overexpression, and KRAS mutated versus wild type. Within each of category of VDR expression, 1- α -hydroxylase expression, and KRAS mutational status, we will examine the influence of plasma levels of 25(OH)D divided into tertiles on DFS and OS. Tertiles will be utilized instead of quintiles of plasma 25(OH)D to maximize the ability to detect an association within each subgroup. Cox proportional hazards models will be used to calculate HRs and 95% CIs for DFS and OS, adjusted for other prognostic factors. Tests for statistical interaction will be performed by entering into the model the cross-product term of plasma 25(OH)D as a continuous variable with the molecular alteration as a binary variable (overexpressed versus not; mutated versus wild type).

In describing analyses related to gene expression, the genes/transcripts from RNA-seq will be referred to as features. The terms feature, feature expression and expression will also be used interchangeably. The maximum number of features is approximately 24,000. In these discussions, K will denote the number features (among the 24,000) which pass the non-phenotypic filters. The expressions, which are summary measures, are obtained following pre-processing. The background correction algorithm implemented by the BeadStudio software will be employed and quantile normalization will be applied to the background adjusted intensities.

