Adequate power is achieved to detect moderate to large hazard ratios for dichotomous biomarkers or genotypes with prevalence close to 50%. The power estimates at 50% prevalence are approximately correct for biomarkers or genotypes with prevalence $\geq 30\%$ and $\leq 70\%$. For biomarkers or genotypes with prevalence near 20% and, in particular, 10%, larger differences are detectable with adequate power.

Table 6. Approximate DFS hazard ratios (maximum versus minimum hazard under “least favorable configuration”) detectable with 70%, 80%, and 90% power for comparisons of a continuous biomarker categorized by quartiles for all patients and the percent of samples available (2-sided $\alpha=0.01, 0.05, 0.10$). The chi-square non-centrality parameters (ncp) are 20.66, 16.74, 14.16, respectively, 70%, 80% and 90% power, with $\alpha=0.01$; 16.21, 12.73, 10.46, respectively, for $\alpha=0.05$; and 8.67, 10.77, and 14.02, respectively, for $\alpha=0.1$. Exponential survival and an overall event rate of 0.31 (775/2500) are assumed.

	Detectable Hazard Ratio (DFS)		
Power	0.7	0.8	0.9
n (number of events)			
1500 (465)	1.64,1.53,1.47	1.72,1.60,1.54	1.82,1.70,1.64
2000 (620)	1.54,1.45,1.40	1.60,1.50,1.45	1.68,1.58,1.53

With 60 and 80% of samples studied, adequate power is achieved to detect moderate to large hazard ratios for biomarkers categorized by quartiles.

Table 7. Difference in median DFS detectable for a continuous marker categorized by quartiles (Biomarker 1) versus a second dichotomous biomarker (Biomarker 2) with approximate powers of 0.44, 0.68, 0.78, respectively, for 2-sided $\alpha=0.01, 0.05, 0.10$, with 60% of patients submitting samples and approximate powers of 0.61, 0.81, 0.88, respectively, for $\alpha=0.01, 0.05, 0.10$, with 80% of patients submitting samples (logrank test). Exponential survival, equal sample sizes per group, and an overall event rate of 0.31 (775/2500) are assumed.

	Median DFS (years)			
Biomarker 1	Quartile(1)	Quartile(2)	Quartile(3)	Quartile(4)
Biomarker 2				
Absent	8.0	9.0	10.0	11.0
Present	9.0	8.0	7.0	6.0

Moderate to large interaction hazard ratios are detectable with adequate power.

Table 8. Power estimates to detect the difference illustrated in Table 9 for a continuous marker categorized by quartiles versus toxicity (< Grade 3+; \geq Grade 3+) for 60% (ncp=9.2) and 80% (ncp=12.3) of patients submitting samples (chi-square, 2-sided $\alpha=0.01, 0.05$).

	Significance Level	
n	$\alpha=0.01$	$\alpha=0.05$

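### Appendix II, Table 7 gives power for a 3-df quartile interaction, but Section 5.0 tests 25(OH)D by KRAS with one cross-product term; Tables 5 and 3 each carry a small slip

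*Combined protocol and SAP*

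**What the plan says.** All references are to Appendix II (CALGB 150911) unless stated.

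- **Section 6.0, text on the tables.** Table 7 is introduced as the difference detectable for a quartile marker against a dichotomous one: "for example, Vitamin D levels measured by plasma 25(OH)D versus K-ras mutational status".
- **Section 6.0, Table 7.** The caption opens: "Difference in median DFS detectable for a continuous marker categorized by quartiles (Biomarker 1) versus a second dichotomous biomarker (Biomarker 2"). For the smaller sample it states "approximate powers of 0.44, 0.68, 0.78, respectively, for 2-sided $\alpha=0.01, 0.05, 0.10$, with 60% of patients submitting samples". At 80% the three figures become 0.61, 0.81 and 0.88 at the same alphas, and the caption names a logrank test. Its modelling assumptions read: "Exponential survival, equal sample sizes per group, and an overall event rate of 0.31 (775/2500) are assumed". The body lists median DFS by quartile. The first row is "Absent 8.0 9.0 10.0 11.0"; with the second marker present the medians are 9, 8, 7 and 6 years. The closing line describes the effects as interactions.
- **Section 5.0, Objective 1.4.** The interaction of 25(OH)D with VDR, 1-alpha-hydroxylase or KRAS is tested with the "cross-product term of plasma 25(OH)D as a continuous variable with the molecular alteration as a binary variable". Tertiles are used for the estimates within marker strata. Section 5.0 does not use quartiles of 25(OH)D.
- **Section 6.0, Table 5.** For prevalence 0.1, 465 events and hazard ratio 1.4, the three powers are "0.034,0.58,0.70", at alpha 0.01, 0.05 and 0.10.
- **Section 6.0, Table 3.** The caption states one alpha, 0.1, but each cell holds three powers.

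**The concern.** A power statement should describe the test that will be run. Four quartiles crossed with two marker levels give an interaction with (4-1)(2-1) = 3 df. A continuous marker times a binary marker gives one coefficient. The two tests have different power for the same pattern and are sensitive to different alternatives, so someone using Table 7 to judge Objective 1.4 reads the wrong number. At 60% of samples and alpha 0.05, the printed 0.68 falls below the usual 80% benchmark, whereas the planned test may be close to it or above it.

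Tables 5 and 3 are smaller matters. One printed power looks ten times too small, and one caption does not say which alphas its columns belong to.

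**Working it through.** **Inputs.** Events are 465 (60% of samples) and 620 (80%), both at the 0.31 event rate. The medians are those of Table 7, with exponential survival and eight equal cells. KRAS is mutated in about 40% of colorectal cancers (Appendix II, Section 2.4). The reduced DFS target is 696 events (protocol Section 13.1).

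**1. Reproduce Table 7.** Under exponential survival the log hazard ratio, present versus absent, is ln(median absent / median present):

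- Q1: ln(8/9) = -0.118
- Q2: ln(9/8) = 0.118
- Q3: ln(10/7) = 0.357
- Q4: ln(11/6) = 0.606

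The mean is 0.2407 and the sum of squared deviations is 0.2906. With E/8 events per cell, each log hazard ratio has variance 8/E + 8/E = 16/E. The noncentrality is 0.2906 x E/16, which is 8.45 for E = 465 and 11.26 for E = 620.

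| Power at alpha 0.01 / 0.05 / 0.10 | 465 events | 620 events |
|---|---|---|
| Printed | 0.44 / 0.68 / 0.78 | 0.61 / 0.81 / 0.88 |
| 3-df interaction | 0.445 / 0.681 / 0.784 | 0.614 / 0.814 / 0.886 |
| 3-df, unequal events per cell | 0.433 / 0.670 / 0.775 | 0.600 / 0.804 / 0.879 |
| 7-df overall test of the eight cells | 0.638 / 0.830 / 0.898 | 0.818 / 0.934 / 0.966 |
| 1-df, linear quartile scores | 0.629 / 0.828 / 0.896 | 0.782 / 0.919 / 0.956 |

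Only the 3-df versions match, all within about 0.01.

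**2. The 1-df test on the same pattern.** With scores -1.5, -0.5, 0.5, 1.5 (sum of squares 5), the slope is 0.2411 and slope squared x 5 = 0.29056. Nearly all of the 0.2906 is linear trend. The noncentrality is 8.44 and 11.26. Power at alpha 0.05 is Phi(2.906 - 1.960) = 0.83 and Phi(3.355 - 1.960) = 0.92, about 15 and 10 to 11 points above the printed figures.

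**3. Sensitivity of the 1-df power at alpha 0.05.**

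- *KRAS at 40%.* The noncentrality is multiplied by 4 x 0.4 x 0.6 = 0.96, giving 8.11 and 10.81. Power is 0.81 and 0.91 (3-df: 0.66 and 0.80).
- *696 total events, equal cells.* Events are 0.6 x 696 = 417.6 and 0.8 x 696 = 556.8; the noncentrality is 7.58 and 10.11. Power is 0.79 and 0.89.
- *Distribution of 25(OH)D, equal cells, 775 total events.* The documents give none, so these are assumptions. Fit the four log hazard ratios to the marker's quartile means to get a slope b, then use noncentrality E x 0.25 x b squared x Var(marker). A uniform marker gives 9.01 and 12.01 (power 0.85 and 0.93). A normal marker gives 9.77 and 13.02 (power 0.88 and 0.95).

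**4. Table 5.** Power is Phi(ln(HR) x sqrt(p(1-p)E) - z). For HR 1.4, p = 0.1 and E = 465, 0.3365 x 0.3 x 21.56 = 2.177. At alpha 0.01, Phi(2.177 - 2.576) = 0.345 (0.3449 unrounded, so 0.34 to two places). The neighbours compute to 0.586 and 0.703 against the printed 0.58 and 0.70. Of 72 entries, 71 reproduce within 2 points; this is the only failure. The same row prints 0.18 at HR 1.3, and power cannot fall as the hazard ratio rises from 1.3 to 1.4.

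**5. Table 3.** Power is Phi(ln(HR) x sqrt(E/16) - z). For HR 1.5 and 465 events this gives 0.348 / 0.589 / 0.706 at alpha 0.01 / 0.05 / 0.10, against 0.34 / 0.58 / 0.71 printed. All 18 entries fit those three alphas within about 0.01.

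**The case against.** The case for leaving Table 7 alone has substance. The table is labelled approximate and 25(OH)D by K-ras is only an example. No degrees of freedom are printed and the caption refers to a logrank test, so 3 df is an inference from the layout and the reproduction. For the pattern shown, the planned test has more power than printed, so the table's conclusion that sizeable interactions are detectable survives. These points stand and limit the weight of the finding. They do not make the printed figures the power of the Section 5.0 test.

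It is also right that the linear-quartile-score figures are not exactly the planned test either, because Section 5.0 enters 25(OH)D as continuous. They are illustrations, and their assumptions must be stated.

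Three stronger readings might be inferred, and the documents do not support them:

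- *That these powers decide how many samples to assay.* The 60% and 80% are scenarios for how many samples become available from optional participation. Nothing in the plan uses Table 7 to set an assay number.
- *That Objective 1.4 is underpowered because of the mismatch.* For the tabulated pattern the error runs the other way.
- *That the Table 5 and Table 3 slips mislead an analysis.* The first is a visible decimal slip beside 0.58 and 0.70, and the text after Table 5 already warns that only larger differences are detectable at 10% prevalence. The second is an incomplete caption.

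**Conclusion.** The point holds as a mismatch between a stated power and the planned test. Table 7's figures fit a 3-df quartile-by-binary interaction, whereas Objective 1.4 is tested on 1 df. For the near-linear pattern tabulated, the printed alpha-0.05 powers of 0.68 and 0.81 are conservative; the illustrative 1-df figures run from about 0.79 to 0.88 at 60% of samples and from about 0.89 to 0.95 at 80%, varying one assumption at a time. The exact value depends on the unstated distribution of 25(OH)D, the marker prevalence and the event count.

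The reassurance covers only a roughly linear interaction. A single product term can miss a non-linear one, and Table 7 gives no power for the planned test in that case.

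The Table 5 entry should be 0.34, and Table 3's columns are for alpha 0.01, 0.05 and 0.10. Neither correction changes an analysis. Everything here concerns an optional companion study; the primary DFS comparison is not affected. Priority is low.

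**What to change.** 1. Restate Table 7 for the 1-df continuous-by-binary test of Section 5.0. State the assumed distribution of 25(OH)D, the KRAS prevalence and the event count, and recompute at the count actually expected. The figures above are illustrative and should not be copied in as final. The alternative is to keep Table 7 and plan a 3-df quartile interaction test.
2. In Table 5 (prevalence 0.1, 465 events, hazard ratio 1.4, alpha 0.01), change 0.034 to 0.34.
3. In Table 3's caption, list the two-sided alphas as 0.01, 0.05 and 0.10.

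The cost is three table corrections and one short recalculation. If the 1-df test is kept, no data collection or analysis changes.
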